4.1.2 Secondary analysis of primary endpoint

The secondary and exploratory comparisons of pain intensity will be performed for arm A vs. arm C, and arm B vs. arm C respectively. The same statistical analyses will be performed as described above in the primary analysis. (Aim 1)

4.2 Secondary endpoints

The secondary outcomes include the level of use of breakthrough pain medication, pain tolerance and sensitivity, chronic low back pain (CLBP) impact score, neuropathic pain scale (NPS, a sum of 10 pain descriptors), profile of mood states (total mood disturbance scores), Beck Depression Inventory II, ability to learn and recall measured using Hopkins Verbal Learning Test (HVLT), measures of concentration, psychomotor speed, and graphomotor abilities by Wechsler Adult Intelligence Scale -III (WAIS-III) digit symbol test, marijuana subscale (M-scale), motor coordination and speed evaluated by grooved pegboard test. In addition, subjective and psychoactive side effects (e.g., good drug effect, drug high) and measures (e.g., lane tracking, car following) in driving simulation will be examined as secondary outcomes in a substudy, where completers with a valid driver's license will receive acute administration of treatment at the driving simulation visit.

All comparisons of secondary outcomes between arms will be with an order of importance as described above for the primary endpoint: 1) primary comparison: arm A vs. arm B; 2) secondary comparison: arm A vs. arm C; exploratory comparison: arm B vs. arm C. No correction will be done for multiple comparisons.

4.2.1 Comparison of outcomes measured at 6 visits between treatment arms

The similar analysis strategies as described above for primary endpoint will be used for the secondary outcomes measured at 6 visits. Briefly, the interaction effect of treatment arm and time (6 visits) on outcome will be tested using a covariance pattern model (e.g., unstructured model). Average change at the treatment period (weeks 5-8) from baseline will be compared between the groups. Non-significant interaction terms will be removed from the models (Aim 2).

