4.1.1 Primary analysis

The primary analysis will be the comparison of self-reported pain intensity between arm A and arm B. An intent-to-treat analysis will be performed on data from participants who complete baseline. Data transformation (e.g., log10, square root) may be performed to improve distribution normality as appropriate. Response profiles analysis will be performed if the trend of pain intensity over time is not linear. We will compare different covariance pattern models (e.g., unstructured, compound symmetry) based on AIC and identify a covariance model with the best fit to our data. This is a randomized controlled trial so that we can remove main group effect with assumptions about equal mean responses (i.e., pain scores) at baseline for the three treatment arms. Weekly or biweekly average of pain intensity from the daily diary will be calculated as a primary outcome. Time will be treated as a factor with 6 levels (i.e., baseline, weeks 1, 3, 5, 7, 8), and the mean response profiles will be compared between the arms. The treatment effect over time will be assessed by the significance of the treatment arm x time interaction using Wald test. Also, average change at the treatment period (weeks 5-8) from baseline will be compared between the groups. (Aim 1)

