4.2.4 Comparison of driving performance between treatment arms

The driving simulation assessments will be conducted in the substudy. (1) Driving measurements (standard deviation of lateral deviation (SDLP) for lane tracking and coherence for car following) following 8 weeks of study medication administration will be compared between treatment arms using ANOVA, to determine whether driving skills will be different after stable cannabis treatment. Acute cannabis effects will be then tested using a covariance pattern model (e.g., unstructured model) including fixed effects of treatment arm, time (minutes), and their interaction. (2) We will also include terms for pain (separately using intensity and relief), its interaction with treatment, and time too, the latter to test for recovery of the cannabis effect back to the Hour 1 baseline level. (3) The correlation (Pearson or Spearman, as appropriate) between blood $\Delta 9$ -THC and each of SDLP and coherence will be estimated at each hour using a 95% confidence interval applied to the Fisher Z-transformation, then back-transformed. Secondary analyses will use independent t-tests or Wilcoxon rank sum tests to compare differences between the means of each of coherence and SDLP for high and low blood $\Delta 9$ -THC levels split at 7 ng/ml. (Aim 3)

4.3 Exploratory analysis:

4.3.1 We will assess the association of daily pain intensity and the dose of treatment (mean daily number of puffs or pills) using a mixed-effects model including fixed effects of dose, treatment regimen, time (i.e., day or week), and dose x treatment regimen interaction, and subject-specific random effect. A significant interaction indicates the association of the dose and pain intensity differs in the three treatment arms. Use of breakthrough pain medication will be then included in the model to remove its confounding effect if it's present. A Non-significant interaction will be removed from the models.

- 4.3.2 Cumulative distributions of maximal pain reduction from baseline among treatment groups will be compared using Kolmogorov-Smirnov tests. This test (nonparametric) will indicate if a given treatment is likely to produce more overall pain reduction than another treatment regimen and takes into account an expected delay in effects of dronabinol compared to whole plant cannabis.

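### SAP 4.2.1 removes non-significant arm-by-time terms, but without them the model cannot give the weeks 5-8 change-from-baseline comparison that the same section promises

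*SAP*

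**What the plan says.** SAP 4.2.1 covers the secondary outcomes measured at the six visits. It takes its method from the primary endpoint: "The similar analysis strategies as described above for primary endpoint will be used for the secondary outcomes measured at 6 visits". It tests arm by time in a covariance pattern model, promises that "Average change at the treatment period (weeks 5-8) from baseline will be compared between the groups", and closes with "Non-significant interaction terms will be removed from the models (Aim 2". It does not list its fixed effects, and it does not say which model supplies the weeks 5-8 comparison.

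The borrowed section, SAP 4.1.1, settles three things:

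- Baseline is a modelled response: "Time will be treated as a factor with 6 levels (i.e., baseline, weeks 1, 3, 5, 7, 8".
- The treatment effect is the interaction: "The treatment effect over time will be assessed by the significance of the treatment arm x time interaction using Wald test".
- The arm main effect may be left out: "This is a randomized controlled trial so that we can remove main group effect with assumptions about equal mean responses".

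Section 4.1.1 has no removal rule. Section 4.2.4, on driving, does list its terms ("including fixed effects of treatment arm, time (minutes), and their interaction"). Section 4.3.1 has a similar rule ("A Non-significant interaction will be removed from the models"), but for dose by regimen in a model whose main effects are listed.

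**The concern.** Dropping a non-significant interaction is harmless when the main effects still answer the question. Here they do not. With baseline among the responses, arm by time is the only part of the model that can carry a between-arm difference in change from baseline. The rule removes that part whenever its test is non-significant.

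The outcomes at stake are the impact score, the Neuropathic Pain Scale, cold pressor sensitivity and tolerance, POMS, BDI-II, HVLT, Digit Symbol, Grooved Pegboard and the M-scale. If the rule is applied before the comparison is made, outcomes with a significant interaction keep visit-specific effects. The others get no arm effect, or a coefficient that is not change from baseline. Results across the secondary outcomes would then describe different quantities, chosen by a p-value. For the Aim 2 mood and cognitive measures, a zero imposed by the model could be read as evidence of no side-effect difference.

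**Working it through.** **Structure (no assumed numbers).** For two arms, write the difference at visit t as Δ(t) = α + γ(t), with γ(0) = 0. Here α is the arm main effect and γ(t) the arm-by-time terms. The promised comparison, using the treatment-period visits at weeks 5, 7 and 8, is

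θ = [Δ(5) + Δ(7) + Δ(8)]/3 − Δ(0) = [γ(5) + γ(7) + γ(8)]/3.

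- Full model: θ is estimable, with or without α.
- Interaction removed, α also left out (as 4.1.1 allows): no arm term remains.
- Interaction removed, α kept (as in 4.2.4): θ = (α + α + α)/3 − α = 0.
- Single arm-by-visit coefficients removed: each one dropped among weeks 5, 7 and 8 contributes 0 to θ, so θ is partly forced to zero.

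Generalised least squares fits to simulated three-arm data (33 per arm) agree. The full model gave A−B = −0.536, A−C = −0.737 and B−C = −0.201. Both reduced models gave 0.000 for all three.

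**The SAP's own effect size.** SAP 5.1 gives 80% power at d = 0.54 (33 per arm) and 0.58 (29 per arm), on the scale of week-8 change. The slope-difference formula is D = 8·√[2(1.96+0.842)²(1−ρ)/(n·S)], with S = 52 for weeks 0, 1, 3, 5, 7, 8. At an assumed ρ = 0.5 it gives 0.541 and 0.577, so both figures reproduce.

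**What the surviving arm coefficient measures.** Assumptions, since the documents give none: compound symmetry, ρ = 0.3/0.5/0.7, and a week-8 difference D = 0.54·√[2(1−ρ)] = 0.639/0.540/0.418 outcome SDs. Under compound symmetry the coefficient is the plain mean of Δ over all six visits.

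| Effect shape | Mean over 6 visits | True θ | Ratio |
|---|---|---|---|
| Linear to week 8 | (24/8)/6·D = 0.500D | (20/3)/8·D = 0.833D | 60% |
| Rise to week 4, then flat | (0.25+0.75+3)/6·D = 0.667D | D | 67% |
| Constant from week 1 | 5/6·D = 0.833D | D | 83% |
| Starts at week 5 | 3/6·D = 0.500D | D | 50% |

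For the first three shapes true θ runs from 0.349 (linear, ρ = 0.7) to 0.639 (plateau or constant, ρ = 0.3), against exactly 0 from the reduced model. With AR(1) by visit order and ρ from 0.3 to 0.9, the ratios for those shapes are 54-79%.

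**How often the term would be removed.** The Wald test is treated as noncentral chi-square at 5% with known covariance and 33 per arm. The equal-baseline form uses the post-baseline covariance given baseline; the arm-kept form uses changes from baseline. Probability that the A-B test (5 df) is non-significant although the effect is real:

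| Shape | Equal baseline, ρ = 0.3/0.5/0.7 | Arm kept (any ρ) |
|---|---|---|
| Linear | 0.237/0.329/0.389 | 0.447 |
| Plateau | 0.101/0.198/0.277 | 0.364 |
| Constant | 0.056/0.169/0.289 | 0.434 |
| Starts at week 5 | 0.066/0.099/0.124 | 0.149 |

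The SAP does not say whether the test is pairwise or three-arm. For a three-arm 10-df test and the first three shapes, equal baseline then arm kept: placebo equal to B, 4-37% and 35-44%; equal steps A-B-C, under 1% and 0.4-1.3%; placebo midway between A and B, 12-52% and 50-58%.

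**The case against.** The strongest reply is the order of the sentences. Section 4.2.1 tests the interaction, makes the weeks 5-8 comparison, and only then mentions removal. In 4.1.1 the same comparison is an addition to the interaction test. A reader may fairly take it from the full model or from a separate change-score analysis, and it is then valid. This stands as a possible reading. The SAP does not state it, though, and under it any arm effect reported from the reduced model is still not change from baseline.

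A model with no arm term at all is also unlikely in a section meant to compare arms. That is fair, but keeping the arm term gives the same zero. If baseline were a covariate, a retained arm term would be a usable post-baseline difference; the SAP does not describe that model.

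The removal frequencies are soft. They turn on effect shape, correlation, the form of the test and the sample size. With 40 per arm as an upper bound for the intent-to-treat set, the A-B ranges for the first three shapes fall to about 2-29% (equal baseline) and 27-35% (arm kept). The frequencies show that removal can be common; they do not fix a rate. Finally, the affected outcomes are secondary and no multiplicity-controlled claim rests on them, which limits the consequence.

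**Conclusion.** The rule is wrong as written for the secondary outcomes at the six visits, and should be fixed. That θ is zero or has no arm term once the interaction is removed follows from the algebra. It needs only that baseline is a modelled time level, as 4.1.1 states, and that the interaction is removed as a whole; removing single terms gives a partial version of the same fault.

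The other sizes are conditional. The surviving coefficient is 60-83% of the true effect under compound symmetry for the first three shapes, and 50% for an effect that starts at week 5. Removal in the A-B test has probability 6-39% (equal baseline) or 15-45% (arm kept) over the four shapes at 33 per arm.

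Confidence is medium, because the SAP can be read as taking the comparison from the full model. The primary endpoint (4.1.1, 4.1.2) and the area-under-the-curve analysis (4.2.3) are not affected.

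**What to change.** In SAP 4.2.1, delete the sentence that removes non-significant interaction terms and keep arm by time whatever its p-value. Add one sentence saying that the weeks 5-8 change-from-baseline contrasts (A−B, A−C, B−C, each with a 95% confidence interval) are estimated from that full model, with baseline handled as in 4.1.1.

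Naming the full model alone would protect the promised comparison. Deleting the rule as well prevents an arm effect being reported from a reduced model, and brings 4.2.1 into line with the primary analysis. The cost is one SAP sentence deleted and one added, with no new data and no burden on participants.

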4.2.2 Comparison of cannabis withdrawal scale between treatment arms

Cannabis withdrawal intensity and negative impact of withdrawal will be assessed via telephone calls at week 8 and week 10. Linear regression will be used to compare changes in intensity and negative

impact of withdrawal symptoms from week 8 to week 10 between the arms.

4.2.3 Comparison of subjective and psychoactive side effects between treatment arms

Psychoactive effects will be assessed at 1, 2, 3, 4, 5, and 6 hours after the first acute administration of treatment at the driving simulation visit in a substudy. Area under the time concentration curve (AUC) will be used as a measure for the aggregate effect of response over a period of time (during 1-6 hours after the 1st dose). AUC will be compared between the arms using linear regression (Aim 2).

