If already using cannabis, participants will be asked to slowly taper cannabis use over a one-week period (Baseline Week - Figure 1) so that they are only using study medications during the remaining 10 weeks of the clinical trial. If unable to abide by this, subjects will not be allowed to participate in the study. Participants will be asked to abstain from cannabis 7 days prior to study entry. In order to ensure abstinence, we will use the Draeger 5000 saliva screening test for tetrahydrocannabinol at their first experimental visit to ensure that they have adhered to this period of abstinence before the study. A level above 5 ng/ml will indicate recent use and the appointment will be rescheduled.

Baseline Period:

If eligibility criteria (see below) are met, subjects will be instructed on completing a paper diary (Appendix 4). Provided their VAS pain intensity remains above 3/10 during the Baseline Week, they will be given oral and herbal study medication (and a Volcano Vaporizer) at the next study visit one week later.

At the baseline visit, participants will be given the Beck Depression Inventory (BDI-II) in order to screen for depression and suicidality. They will also be given the AUDIT and DAST to screen for substance use problems. The PSQ and Mood Disorder Questionnaire will also be administered to screen for Schizophrenia and Bipolar Type I, respectively. The painDETECT Questionnaire will be administered to distinguish neuropathic low back pain from non-neuropathic low back pain. The Survey of Cannabis Use will be administered during this period to obtain information on the cannabis use habits of the participant.

Should the participant choose to participate in the driving simulation portion of the study, the Driving History and Habits Questionnaire will be administered to obtain information on participant driving history, should they decide to participate in the driving simulation study portion.

Telephone Interview:

To determine eligibility, each prospective participant will be asked the following questions from the NIH Chronic Low Back Pain Definition:

1. Do you have low back pain?

No	STOP.....	0
Yes		1

2. How long has low back pain been an ongoing problem for you?

Less than 1 month	0
1-3 months	1
3-6 months	2
6 months -1 year	3
1-5 years	4
More than 5 years	5

3. How often has low back pain been an ongoing problem for you over the past 6 months?

[figure not shown]
Every day or nearly every day in the past 6 months	0

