10. HUMAN SUBJECTS

Total number of participants to be enrolled: This will be a single site study with 120 participants enrolled at UCSD.

Age: Because of the problems inherent in the use of cannabis in children and adolescents, we will not enroll individuals below the age of nineteen. Frequent use can affect school performance and relationships with family members in younger individuals ^{42, 43}. Earlier and greater involvement with marijuana has also been associated with increased risk of poor mental health ^{44, 45}.

Gender: Both male and female populations develop chronic low back pain (CLBP); however, there is a tendency towards a higher incidence in males.

Ethnic background: CLBP is ubiquitous. Global studies have shown that low back pain is one of the most common complaints that patients bring to their physicians ^{46, 47}. Given the diverse ethnic background of San Diego, we should be able to recruit subjects from multiple ethnic backgrounds. A neuropathic component has been found in approximately 37% of patients with CLBP ⁴⁸; given the relative frequency of the latter, we should not encounter difficulty recruiting 120 participants.

Health status: Individuals with significant cardiovascular, hepatic or renal disease, uncontrolled hypertension, and chronic pulmonary disease (eg, asthma, COPD), will be excluded. This will be operationalized using criteria from the literature on adverse effects of medicinal cannabis ^{49, 50}.

Inclusion criteria

- Age greater than 18
- Presence of chronic low back pain (CLBP) defined as the response to two questions 1) How long has back pain been an ongoing problem for you? 2) How often has low back pain been an ongoing problem for you over the past 6 months? A response of greater than 3 months to question 1 and a response of "at least half the days in the past 6 months" to question 2 will define CLBP according to the NIH Task Force on Research Standards for Chronic Low Back Pain (Appendix 15). ⁹
- Visual average numerical pain intensity greater than 3/10 during one-week observation period
- To avoid confounding by concurrent medications and/or prior cannabis exposure, participants will have had a stable analgesic regimen that they will continue throughout the study and not having used cannabis for more than 7 days prior to study entry. The latter criteria will be verified by the use of the Draeger test at the first experimental visit.

Exclusion criteria

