5.1 Power Estimation

Power estimates for each outcome assumed a 5% significance level. Totally, N=120 subjects will be randomized in 1:1:1 ratio to the three treatment arms, that is, 40 subjects to each arm. Using the same 16% drop-out rate experienced in our previous study and that 87% of the completers possess a valid driver's license, a national average published by the Department of Transportation, power was calculated for 33 subjects per treatment arm (total N=99) for Aims 1 and 2, and 29 subjects per treatment arm (total N=87) for Aim 3. We have 80% power to detect effect sizes equivalent to Cohen's $d=0.54$ and $d=0.58$ for sample sizes 33 and 29 respectively. This effect size is based on differences between groups of changes from baseline at the end of the study (week 8). The power is calculated using specific formulas for a time-by-treatment interaction in a longitudinal linear mixed-effects model {Diggle PJ, Heagerty P, Liang KY, Zeger SL: Analysis of Longitudinal Data, 2nd edition, 2002, Oxford University Press, Oxford, p.29}. Power is expected to be higher for larger effect sizes and fewer dropouts.

6. Data and Safety Monitoring Committee (DSMC)

Progress reports will be presented to the DSMC every 6 months. Two reports (open and closed reports) will be generated and presented in two sessions.

Key study personnel and all DSMC members will attend the open session; *the open report* will present data in aggregate form (not by arm). Open session attendees will review presented summarized data for data completeness and accuracy (e.g., review ranges for numeric variables to catch any outliers/unusual observations).

The closed session will include only the study statistician and members of the DSMC; *the closed report* will present data by treatment arm, but in blinded fashion,

i.e., arms will be presented as arm X, arm Y, arm Z. Treatment labels can be revealed to the DSMC members upon their request if major concerns arise. Statistical comparison of relevant characteristics between the arms will be done. No interim analysis comparing primary outcomes between the arms will be performed in order to preserve the power of the primary analysis and the overall Type I error at 0.05 level till the end of the study, unless requested by the DSMC. Members of the DSMC will be asked to maintain confidentiality related to the interim data presented in the closed report until the end of the trial.

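### The psychoactive AUC regression and the week-8 driving ANOVA leave out prior cannabis use, which is recorded before study drug; the cost is precision, of unknown size, and not bias.

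*SAP*

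**What the plan says.** **Outcome models.** SAP 4.2.3 summarises the psychoactive ratings after the first acute dose as an area under the curve and states: "AUC will be compared between the arms using linear regression (Aim 2"). No covariate is named. SAP 4.2.4 item 1 compares lane weaving (SDLP) and car-following coherence after 8 weeks by ANOVA between arms, again with no covariate. It continues: "Acute cannabis effects will be then tested using a covariance pattern model", with arm, time and their interaction as fixed effects.

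**What is recorded beforehand.** Protocol section 9 (Baseline Period) states: "The Survey of Cannabis Use will be administered during this period to obtain information on the cannabis use habits of the participant". This comes before study medication is handed out. Section 9 also lets current users enter after a one-week taper, so prior use will differ between participants. The driving part includes a baseline session before Week 1.

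**How the protocol treats prior use.** The inclusion criterion in section 10 on stable analgesics and 7 days without cannabis opens: "To avoid confounding by concurrent medications and/or prior cannabis exposure". The documents describe 1:1:1 allocation and mention no stratification factor.

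**What has no baseline.** In Protocol Table 3, pain score, vital signs and driving are measured at Hour 1, before the first dose. Psychoactive effects are first rated at Hour 2, after it.

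**The concern.** Seven days of abstinence clears recent drug. It need not equalise experience, tolerance or expectation, all of which could affect how someone rates feeling high or liking the drug. Any such variation stays in the residual of a regression on arm alone.

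The two analyses named here are the most exposed. Each uses a single value per person, neither contains a pre-treatment measure of its outcome, and the substudy is planned at 29 per arm. For the AUC, prior use is the obvious available baseline covariate, because no pre-dose rating exists. For the driving ANOVA, the baseline drive is also at hand and is not used.

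The choice should be made in advance. SAP 2.1 tests baseline characteristics between arms, and adding a covariate only after seeing an imbalance would be a data-driven decision.

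**Working it through.** **Inputs.** From SAP 5.1: 5% significance level, 80% power, 33 per arm for Aims 1 and 2, 29 per arm for Aim 3 (33 × 0.87 = 28.7), and detectable d of 0.54 and 0.58. Although 4.2.3 is labelled Aim 2, its ratings are taken at the driving visit among licence holders, so 29 is the relevant number. Not in the documents: sidedness (taken as two-sided), the within-person correlation ρ, the share of prior users p, and their outcome difference δ.

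**Step 1. Reproduce the SAP figures.** SAP 5.1 says they come from a time-by-treatment formula. Under compound symmetry, d² = 2(z₀.₉₇₅ + z₀.₈₀)²(1 − ρ)T² / [n Σ(t − t̄)²]. The times in SAP 4.1.1 are 0, 1, 3, 5, 7 and 8 weeks, so T = 8, t̄ = 4 and Σ(t − t̄)² = 16 + 9 + 1 + 1 + 9 + 16 = 52. With ρ = 0.5 (assumed):

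- n = 33: d² = 2 × 7.849 × 0.5 × 64 / (33 × 52) = 0.293, d = 0.541
- n = 29: d² = 2 × 7.849 × 0.5 × 64 / (29 × 52) = 0.333, d = 0.577

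Both agree with the SAP. They apply to a change over repeated visits.

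**Step 2. Detectable difference for a single-value contrast.** The AUC and the week-8 ANOVA use one value per person. The standard error of a two-arm difference is √(2/29) = 0.263 SD, so the detectable d is (1.960 + 0.842) × 0.263 = 0.736. Power at d = 0.58 is Φ(0.58/0.263 − 1.960) = 60%.

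**Step 3. Add a covariate.** A baseline covariate explaining a share R² of within-arm variance multiplies the detectable d by √(1 − R²). These are normal approximations and ignore the degree of freedom spent.

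| R² | Detectable d, 29 per arm | Power at d = 0.58 | Equivalent n per arm, 29/(1 − R²) |
|---|---|---|---|
| 0 | 0.736 | 59.8% | 29.0 |
| 0.01 | 0.732 | 60.3% | 29.3 |
| 0.04 | 0.721 | 61.6% | 30.2 |
| 0.09 | 0.702 | 63.9% | 31.9 |
| 0.25 | 0.637 | 72.3% | 38.7 |

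For a yes/no covariate with δ in outcome SDs, R² = p(1 − p)δ². Users at 20% with δ = 0.25 give 0.16 × 0.0625 = 0.01; 20% with δ = 0.5 give 0.04; 50% with δ = 1.0 give 0.25. The last is a generous upper end.

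**Step 4. Chance imbalance.** With an assumed 40% users, two arms of 29 differ in user share by 15 percentage points or more in 22.7% of trials (exact binomial). With δ = 0.8, a 15-point difference moves the contrast by 0.15 × 0.8 = 0.12 SD. That is 0.12/0.263 = 0.46 of a standard error, and the unadjusted standard error already allows for it.

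**Step 5. Pain, for comparison.** Under the compound-symmetry slope formula of step 1, a covariate that is constant over time and entered as a main effect leaves the variance of the arm-by-time contrast unchanged (ratio 1.000). For the week-8 contrast with baseline means constrained equal (ρ = 0.5, 33 per arm), correlations r of 0.1, 0.3 and 0.5 between prior use and pain give variance ratios of 0.997, 0.967 and 0.889. Detectable d goes from 0.597 to 0.596, 0.587 and 0.563.

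**The case against.** The strongest reply is that nothing is invalid. Under randomisation the unadjusted contrasts are unbiased, and their standard errors cover chance imbalance. That stands, and it limits the point to efficiency.

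Three stronger readings are tempting, and the documents do not support them.

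- **The arm comparisons are confounded.** A reader might infer this from the protocol's own word. In context, that word gives the reason for an eligibility rule. It is not a statement about the randomised contrasts, and no covariate is promised.
- **Every interval is wider than it need be, including the one for pain.** The pain model already holds baseline pain, with "The treatment effect over time will be assessed by the significance of the treatment arm x time interaction using Wald test", and step 5 shows little or no gain there. The acute driving model tests arm by time from a pre-dose Hour 1 drive at the same visit, and the withdrawal analysis uses a change from week 8 to week 10. Stable differences between users and non-users largely cancel in both.
- **The SAP's 0.58 shrinks by √(1 − R²).** That figure reproduces from a slope formula, where a time-constant main effect changes nothing. The starting point for these two analyses is 0.736.

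Other parts of the reply also carry weight. Abstinence is not the only safeguard: section 10 excludes on a drug-use screening score and on a urine screen that includes THC unless prescribed, and section 9 excludes those who cannot keep to the taper. These rules may narrow the range of prior use. The ratings are also taken after 8 weeks of study medication, and the leading comparison is between two THC arms, so earlier tolerance may matter less by then. Both considerations make the lower rows of R² plausible. Neither removes the case for a covariate that is already collected.

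**Conclusion.** The point holds for two analyses: the psychoactive AUC (SAP 4.2.3) and the week-8 driving ANOVA (SAP 4.2.4 item 1). Both omit a relevant variable recorded before study drug. The AUC has no baseline rating to fall back on, and the driving ANOVA ignores the baseline drive.

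The loss is precision only. On the assumed range of R² from 0.01 to 0.25, adjustment lowers the detectable difference by between 1 − 0.732/0.736 = 0.5% and 1 − 0.637/0.736 = 13%. That range is an assumption throughout, because the documents give neither user share nor user effect. If prior use is only weakly related to the outcome, the gain is negligible. No stated figure in the SAP is wrong on this account, and the primary pain analysis is not put in doubt.

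**What to change.** - **SAP 4.2.3:** add baseline prior cannabis use as a main-effect covariate in the AUC regression.
- **SAP 4.2.4 item 1, week-8 comparison:** replace the ANOVA by an analysis of covariance with prior use and the matching measure from the baseline drive. The table in the working then applies to the R² of both covariates together.
- **Coding:** define the prior-use variable from the Survey of Cannabis Use in the SAP before unblinding. The survey's items are not in the text available, so the sponsor must choose the coding. A simple one, such as current use before the taper (yes/no), would do if the survey supports it.
- **Sensitivity:** report the unadjusted models alongside.
- **Pain and the other repeated-measures outcomes:** adjustment, as prior use plus prior use by time, is an optional sensitivity analysis.
- **Arm-by-prior-use tests:** not proposed, since about 29 per arm offers little information on an interaction.

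The cost is SAP wording and one degree of freedom per covariate. No new data are needed. The downside is little gain if the covariate proves weak, and a rule is needed for participants with a missing survey or baseline drive.
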